5.2 Subject Exclusion Criteria

Subjects presenting with any of the following must not be included into the study:

1. History of allergy to drug in the iminosugar class;
2. Treatment with any investigational products or therapies within 30 days (or 5 half-lives, whichever is greater) prior to the first day of dosing;
3. Currently has, or has a history of, disease or dysfunction of the pulmonary, cardiovascular, endocrine, hematologic, neurological, immune, GI, genitourinary, or other body system, that is likely to affect the safety of the subject;
4. Creatinine clearance < 90 mL/min (based on Cockcroft-Gault equation);
5. Proteinuria greater than or equal to 1+;
6. At screening, Grade 1 or higher abnormalities in supine vital signs to include deviations in temperature, resting heart rate, blood pressure, and respiratory rate (may be repeated once); at check-in (Day -1), Grade 2 or higher abnormalities in supine vital signs (see [Appendix II](#)). A second set of values were added to the toxicity table for subjects who present with asymptomatic bradycardia at baseline at time of screening (<60 bpm);
7. Abnormalities of physical exam suggestive of conditions that would pose an increased risk to the subject;
8. Abnormal ECGs; however, abnormal readings for the following benign conditions will be acceptable for the study: sinus bradycardia, sinus arrhythmia, early repolarization, nonspecific ST-T wave pattern or changes, right axis deviation (axis 100 degrees or less), first degree AV block (PR interval less than 210ms), nonspecific intraventricular

conduction delay (QRS less than 120ms), indeterminate axis, and short PR interval (where no delta wave).

If an abnormal ECG finding is previously recorded, medically insignificant, and attributed to other causes (i.e. body habitus), Principal Investigator (PI) may elect to enroll the subject.

9. At screening, laboratory values outside of the normal range; however, the following list of parameters (see below table) are not considered exclusionary if values fall outside of the normal range. At baseline/check-in (Day -1), values that are Grade 2 or higher based on the toxicity grading scale ([Appendix II](#)).

Low Chemistry Values	High Chemistry Values	Urinalysis	Hematology Values	Low Coagulation Values
Alkaline Phosphatase	Chloride	High or low specific gravity	Low-Basophils	PT
AST	CPK less than 400 (CO2)	High or Low pH	Low-Eosinophils	aPTT

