9.1.2 Vital Signs

Vital signs (after being supine for 10 minutes) including SBP and DBP (mmHg), pulse rate (beats/minute), respiratory rate (breaths/minute), and oral temperature ($^{\circ}\text{C}$) will be obtained and recorded according to the time points in the schedule of events ([Appendix IV](#)). Systolic and diastolic blood pressure and pulse rate will also be obtained after 2 minutes standing and recorded according to the time points in the schedule of events. If a vital sign measurement is observed to be abnormal, it may be repeated up to a total of 2 times at 5 to 10 minutes intervals. If a normal value is obtained, no further repeat measurements are required. If the value is still abnormal after 2 repeats, the least abnormal value will be utilized for grading the AE. The AE will be considered ongoing until a future measurement shows resolution. The subject may be referred to a primary care provider if the abnormality does not resolve and, according to the study clinicians, requires medical care. Vital sign values of Grade 1 or higher according to toxicity grading criteria listed in [Appendix II](#) will be reported as AEs.

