9.2 Methods and Timing for Assessing, Recording, and Analyzing Safety Parameters

9.2.1 Adverse Events

ICH E6 defines an AE as any untoward medical occurrence in a patient or clinical investigation subject administered a pharmaceutical product regardless of its causal relationship to the study treatment. An AE can therefore be any unfavorable and unintended sign (including an abnormal laboratory finding), symptom, or disease temporally associated with the use of a medicinal (investigational) product. The occurrence of an AE may come to the attention of study personnel during study visits and interviews of a study recipient presenting for medical care, or upon review by a study monitor.

All AEs including local and systemic reactions not meeting the criteria for “SAEs” should be captured on the appropriate eCRF. Information to be collected includes event description, time of onset, clinician’s assessment of severity, relationship to study product (assessed only by those with the training and authority to make a diagnosis, which would include Medical Doctor, Physician’s Assistant, Nurse Practitioner, Doctor of Osteopathy, or Dentist), and time of resolution/stabilization of the event. All AEs occurring while in study must be documented appropriately regardless of relationship. All AEs will be followed to adequate resolution as determined by the PI.

Any medical or laboratory condition that is present at the time that the subject is screened up through ingestion of the first dose should be considered as baseline/pre-existing condition and not reported as an AE. However, if it deteriorates at any time during the study after ingestion of the first dose, it should be recorded as an AE.

All AEs must be assessed for severity and relationship to study product. The PI will make an assessment of severity for each AE and SAE reported during the study and will assign it to one of the following categories:

Mild: An event that is easily tolerated by the subject, causing minimal discomfort and not interfering with everyday activities;

Moderate: An event that is sufficiently discomforting to interfere with normal everyday activities;

Severe: An event that prevents normal everyday activities

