The collection of laboratory data is listed in [Section 8.2.1](#). The normal reference ranges utilized in this study are shown in the current version of the Laboratory Protocol Reference Ranges published by Lab. The grading of abnormal clinical findings are based on the FDA Guidance for Industry: *Toxicity Grading Scale for Healthy Adult and Adolescent Volunteers Enrolled in Preventive Vaccine Clinical Trials September 2007* and *Division Of Microbiology And Infectious Diseases (DMID) Adult Toxicity Table November 2007* as modified for this study (see [Appendix II](#)).

Any medical condition or graded laboratory value (according to [Appendix II](#)) after ingestion of the first dose or deterioration from the baseline condition will be reported and followed as an AE or, as appropriate, SAE. Attempts will be made to follow the subject closely to determine the outcome and duration of an event. Additional assessments including the repeat of laboratory tests and ECGs will be performed in an effort to monitor the subject as appropriate. If an event is ongoing at the time of study termination, permission will be requested from the subject to continue follow-up until the site PI or designee deems the event to be resolved, chronic, or the subject's condition to be medically stable. Abnormal ECGs, at the discretion of the PI, will be reviewed by a cardiologist.

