APPENDIX I SUBJECT FLOWDOWN

APPENDIX II UV-4B TOXICITY GRADING CRITERIA FOR NORMAL HUMAN SUBJECTS

Vital Signs*	Mild (Grade 1)	Moderate (Grade 2)	Severe (Grade 3)	Potentially Life Threatening (Grade 4)
Fever (°C)** (°F)**	38.0 – 38.4 100.4 – 101.1	38.5 – 38.9 101.2 – 102.0	39.0 – 40 102.1 – 104	>40 >104
Tachycardia – (beats per minute)	101 – 115	116 – 130	>130	Emergency room visit or hospitalization for arrhythmia
Bradycardia – (beats per minute)	50-54 if baseline >60	45-49 if baseline >60	<45 if baseline >60	Emergency room visit or hospitalization for arrhythmia
	45-50 if baseline ≤ 60	40-44 if baseline ≤ 60	<40 if baseline ≤ 60	
Hypertension (systolic) – mmHg	141 – 150	151 – 155	>155	Emergency room visit or hospitalization for malignant hypertension
Hypertension (diastolic) – mmHg	91 – 95	96 – 100	>100	Emergency room visit or hospitalization for malignant hypertension
Hypotension (systolic) – mmHg	85 – 89	80 – 84	<80	Emergency room visit or hospitalization for hypotensive shock
Respiratory Rate – breaths per minute	17-20	21-25	>25	Intubation

AE = adverse event; CRF = case report form
 * Subject should be at rest for all vital sign measurements.
 **Oral temperature; no recent hot or cold beverages or smoking
 All graded values representing a change from baseline must be reported as AEs. For clinical or laboratory observations not addressed by the toxicity grading criteria, Grade 0 = absent will be used in the AE CRF to indicate the toxicity grading criteria do not apply.

Systemic (General)	Mild (Grade 1)	Moderate (Grade 2)	Severe (Grade 3)	Potentially Life Threatening (Grade 4)
Nausea/vomiting	No to mild interference with activity or 1 to 2 episodes/24 hours	Moderate interference with activity or >2 episodes/24 hours	Prevents daily activity, requires outpatient IV hydration	Emergency room visit or hospitalization for hypotensive shock
Diarrhea	2 - 4 loose stools or < 400 gm/24 hours	5-6 stools or 400 – 800 gm/24 hours	7 or more watery stools or > 800gms/24 hours or requires outpatient IV hydration	Emergency room visit or hospitalization
Headache	No interference with activity	Repeated use of non-narcotic pain reliever > 24 hours or some interference with activity	Significant; any use of narcotic pain reliever or prevents daily activity	Emergency room visit or hospitalization
Fatigue	No interference with activity	Some interference with activity	Significant; prevents daily activity	Emergency room visit or hospitalization

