10.7.4 Clinical Laboratory Parameters

Observed values and change from baseline data for clinical laboratory parameters (hematology, serum chemistry, coagulation, urinalysis) will be summarized by treatment. Baseline is considered as the last laboratory test result collected before the first dose.

Shift tables will be presented for serum chemistry, hematology, coagulation, and urinalysis parameters according to laboratory toxicity grading. The grading of laboratory findings was based on the *FDA Guidance for Industry: Toxicity Grading Scale for Healthy Adult and Adolescent Volunteers Enrolled in Preventive Vaccine Clinical Trials September 2007* and *Division of Microbiology and Infectious Diseases (DMID) Adult Toxicity Table November 2007* as modified for this study (found in Appendix II of the protocol). A summary of clinical laboratory values of toxicity Grade 1 or higher will also be provided by parameter and treatment.

Individual subject data listings (serum chemistry, hematology, coagulation, and urinalysis) will be provided to summarize all laboratory values including change from baseline, all laboratory values outside the clinical reference ranges, and all laboratory values of toxicity Grade 1 or higher.

Values for any serum chemistry, hematology, coagulation, and urinalysis values outside the clinical reference ranges and also meeting toxicity grading criteria will be flagged on the individual subject data listings.

Fecal and vomitus occult blood findings will be summarized and listed by treatment and study day.

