10.7.5 Vital Signs

Routine vital signs data (systolic and diastolic blood pressure, pulse rate, respiratory rate, and oral temperature) and orthostatic vital signs data (blood pressure and pulse rate) will be listed and summarized by treatment, along with changes from baseline, where baseline is defined as the last value prior to the first dose on Day 1, including unscheduled values. Orthostatic change is the standing value minus the supine value taken prior to the standing value.

A summary of vital signs values of toxicity Grade 1 or higher will also be provided by parameter and treatment. The grading of vital signs was based on the *FDA Guidance for Industry: Toxicity Grading Scale for Healthy Adult and Adolescent Volunteers Enrolled in Preventive Vaccine Clinical Trials September 2007* as modified for this study (found in Appendix II of the protocol).

For routine vital signs data, values outside the clinical reference ranges will be flagged on the individual subject data listing, as will the vital sign values meeting toxicity Grade 1 or higher.

The reference ranges for routine vital signs are: supine systolic blood pressure (90-140 mmHg), supine diastolic blood pressure (50-90 mmHg), supine pulse rate (40-100 bpm), respiratory rate (10-24 breaths/minute) and oral temperature (35.5°C -37.8°C).

Orthostatic decreases of ≥ 20 mmHg for systolic blood pressure or ≥ 10 mmHg for diastolic blood pressure or an increase in heart rate of > 30 bpm are considered to be of potential clinical concern and will also be highlighted on the individual data listings. Repeat and unscheduled readings will be handled as defined in Section 10.1.1.

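### The protocol's AE reporting rules conflict for values already Grade 1 before dosing that do not worsen in grade, and the SAP does not resolve how to count them

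*Protocol*

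**What the plan says.** The protocol gives four triggers for reporting a graded value as an AE:

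- **9.1.2 (vital signs):** "Vital sign values of Grade 1 or higher according to toxicity grading criteria listed in" Appendix II are reported as AEs. No baseline condition is attached.
- **9.2.3 (medical conditions and graded laboratory values):** such a finding "after ingestion of the first dose or deterioration from the baseline condition will be reported and followed as an AE".
- **9.2.1:** a medical or laboratory condition present at any point up to the first dose "should be considered as baseline/pre-existing condition and not reported as an AE", unless it later deteriorates.
- **Appendix II, footnote to each grading table:** "All graded values representing a change from baseline must be reported as AEs". Change is not defined as a change of value or of grade, nor by direction.

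On eligibility, exclusion criterion 6 removes Grade 1 or higher supine vital signs at screening, but later removes only "at check-in (Day -1), Grade 2 or higher abnormalities in supine vital signs". Criterion 9 and section 8.2.1 apply the same Grade 2 threshold to Day -1 laboratory values.

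Protocol 3.2.1 makes AE occurrence and laboratory change from baseline the primary outcome measures. SAP 10.7.2 counts as treatment-emergent any AE arising after the first dose, or one already present that becomes more severe. SAP 10.7.4 adds: "A summary of clinical laboratory values of toxicity Grade 1 or higher will also be provided by parameter and treatment". SAP 10.7.5 adds: "A summary of vital signs values of toxicity Grade 1 or higher will also be provided by parameter and treatment". Grade shift tables are planned for laboratory data only.

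For bradycardia, criterion 6 says a second set of grading values was added for "subjects who present with asymptomatic bradycardia at baseline at time of screening (<60 bpm". Appendix II splits its rows at a baseline above 60 versus 60 or below. SAP 10.1 and 10.7.5 define baseline as the last value before the first dose.

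**The concern.** A site that follows 9.1.2 and a site that follows the Appendix II footnote can handle the same stable Grade 1 vital sign differently, and both would be compliant. The same holds for a stable Grade 1 laboratory value under 9.2.3 and 9.2.1. AE occurrence is the first primary outcome, dose groups have six subjects, and up to two sites enrol. Vital signs are repeated hourly for much of each dosing day, so a subject who starts at Grade 1 has many chances to be recorded. The SAP does not settle the matter. A value reported with a post-dose onset date meets the first limb of the treatment-emergent definition, and the sentence in SAP 10.7.2 on pre-existing conditions mentions only those present at screening.

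**Working it through.** **No figure to reproduce.** The sample size has no statistical basis (SAP 8) and there are no hypotheses (Protocol 11.1). The check applies each rule as written to the same pair of grades.

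| Baseline to post-dose | 9.1.2 (vital signs) | 9.2.3, literal (laboratory) | 9.2.1 | Appendix II footnote |
|---|---|---|---|---|
| Grade 0 to 1 | AE | AE | AE | AE |
| Grade 1 to 1, same value | AE | AE | not AE | not AE |
| Grade 1 to 1, value moved | AE | AE | not AE, if deterioration means a higher grade | AE if change means value; not AE if it means grade |
| Grade 1 to 2 | AE | AE | AE | AE |

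The conflict is confined to the two middle rows. Section 9.2.1 names medical and laboratory conditions but not vital signs. For vital signs the direct clash is therefore between 9.1.2 and the footnote under the vital-sign table.

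**Who can be in those rows.** Screening removes Grade 1 vital signs and most out-of-range laboratory values. Some Grade 1 findings can still pass:

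- Trace urine protein is tolerated when specific gravity exceeds 1.015 (criterion 9), and trace is Grade 1 in Appendix II.
- Urine blood is exclusionary only above 3 RBC/hpf (criteria 9 and 10), and 1-10 is Grade 1. So 1-3 RBC/hpf is eligible and graded.
- A value that was normal at screening can be Grade 1 at Day -1 and remain eligible.

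**Scale, on an assumed prevalence.** Let p be the share of subjects with an unchanged Grade 1 value. The documents give no p; I take 5% to 30%. With six active subjects per cohort (Protocol 11.2), P(at least one) = 1 - (1 - p)^6:

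- p = 0.05: 1 - 0.95^6 = 26.5%
- p = 0.10: 1 - 0.90^6 = 46.9%
- p = 0.20: 1 - 0.80^6 = 73.8%
- p = 0.30: 1 - 0.70^6 = 88.2%

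Expected subjects, both arms together: 24p = 1.2 to 7.2 for three cohorts; 40p = 2 to 12 for five. One subject moves a dose-group rate by 1/6 = 16.7 points. Under a rule that requires a higher grade than baseline, these cases add no AEs.

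**One parameter as a test of p.** Respiratory rate is Grade 1 at 17-20. Assume a usual rate of 14-16 with SD 2-2.5. A single reading of 17 or more has probability P(Z > (16.5 - 14)/2) = P(Z > 1.25) = 10.6% at the low end and P(Z > (16.5 - 16)/2.5) = P(Z > 0.2) = 42.1% at the high end. Section 9.1.2 permits two repeats and grades the least abnormal value. If both are used and readings are independent, all three are 17 or more with probability 0.1056^3 = 0.1% to 0.4207^3 = 7.4%. Positively correlated readings would give a result between the three-reading and single-reading figures.

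**Bradycardia.** Take a pulse of 43. Appendix II makes it Grade 3 (below 45) if baseline is above 60, and Grade 2 (40-44) if baseline is 60 or below. A subject at 58 at screening and 63 just before dosing falls on different sides depending on which measurement is the baseline. Protocol 9.6 halts on any single Grade 3 finding, and 9.7 withdraws the subject.

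**The case against.** **The passages can be read together.** Section 9.1.2 grades by Appendix II, whose footnote limits reporting to changes from baseline. Section 9.2.3 can be read as new after dosing, or worse than baseline, which matches 9.2.1. The Amendment 2 rationale for 9.2.3 also speaks of change from baseline, so its wording is probably a drafting slip. This does not rescue 9.1.2: the rationale given for that sentence is that every Grade 1-4 vital-sign finding is reportable. The footnote also says change rather than worsening, so it does not match 9.2.1 exactly.

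**Over-reporting is the stated default.** Section 9.2.1 says a doubtful observation is to be reported. That helps safety capture, but it leaves the count dependent on how much doubt each site has.

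**The analysis has safeguards.** Laboratory grade shift tables and change-from-baseline summaries show the starting point, and vital-sign changes are a secondary outcome. The Grade 1 or higher tables summarise values and do not feed the AE outcome. All of this stands. It leaves the treatment-emergent AE count unsettled and vital signs without a shift table.

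**Larger magnitudes do not hold.** A reader might take the 26 Table 5 analytes that Appendix II grades, give each a 1% to 5% chance of Grade 1, and infer from 1 - (1 - q)^26 that 23% to 74% of subjects carry one. The documents do not support this. The rate and the independence are assumed, screening is ignored, and several thresholds lie well outside normal (platelets 99,000 or fewer; CPK and alkaline phosphatase at least twice ULN). AEs are tabulated by preferred term, where the same inputs give 8 x 0.01 = 0.08 to 8 x 0.05 = 0.4 carriers per analyte per cohort.

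**Bradycardia.** Criterion 6 explains why a row was added and is not itself a grading rule, and below 60 versus 60 or below differ only at exactly 60. Both are fair. The choice between the screening and the last pre-dose measurement remains open.

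**Conclusion.** The conflict is real and in current text, but narrow. It affects only subjects already Grade 1 before dosing who do not worsen in grade. Their values can enter the treatment-emergent AE counts inconsistently across up to two sites, and they add to the Grade 1 or higher tables in both arms. The prevalence range of 5% to 30% is an assumption; the respiratory example shows how far it depends on use of the permitted repeats.

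Three stronger conclusions a reader might draw are not supported:

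- **That a drug difference is hidden.** The rules apply equally to placebo and no inferential safety analysis is planned (SAP 10.7.8). Dilution is possible but not shown.
- **That the affected values are drug toxicity driving escalation.** An unchanged Grade 1 value meets none of the Grade 2 or Grade 3 criteria in 9.6 or 9.7. Day -1 excludes Grade 2, so a post-dose Grade 2 or 3 is normally a worsening on which all the rules agree.
- **That persistent Grade 1 baselines are common.** Screening removes many, and no frequency is given.

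The bradycardia point is separate. There the baseline can decide between Grade 2 and Grade 3, and so can reach the halting and withdrawal criteria.

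**What to change.** **Protocol.** Reconcile 9.1.2, 9.2.3, 9.2.1 and the Appendix II footnote to one reporting rule that names the baseline measurement and defines change or deterioration by grade. Naming the baseline matters for laboratory data too: 8.2.1 calls Day -1 the baseline, while the SAP uses the last pre-dose value, and a subset of tests is drawn again before dosing on Day 1.

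**SAP.** In 10.7.2, 10.7.4 and 10.7.5, count a laboratory or vital-sign abnormality as treatment-emergent only when its post-dose grade exceeds the baseline grade, with baseline as in SAP 10.1. Keep all graded values in the listings. Add a vital-sign grade shift table. If any cohort has already been dosed, apply the rule to every cohort at analysis so that counts are comparable.

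**Bradycardia.** Criterion 6, the Appendix II rows and the SAP baseline definition must be reconciled. Which measurement should govern is for the sponsor to decide.

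**Cost.** Wording in the next amendment and in the SAP before lock, plus programming to link reported AEs to the graded values. No new data are needed. The downside is that fewer Grade 1 events are counted, including a value that normalises after dosing and then returns to its baseline grade; such values remain visible in the listings.

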9.1.3 Electrocardiograms

A 12-lead ECG will be performed at approximately the same time each day. Subjects will be placed in a supine position for at least 10 minutes prior to recording an ECG. Triplicate 12-lead ECGs will be collected at the pre-dose on Day 1 (baseline) and a single ECG will be collected at other scheduled times. The screening and Day 1 ECG will be used by the PI to determine subject's eligibility for enrollment. The Day 1 ECG will be reviewed to determine if subjects are safe and appropriate to dose and will be used to determine baseline for waveform and QTc.

All ECGs will be reviewed by the PI or designee. ECGs with the following readings will be considered acceptable for study and will not be considered abnormal for study purposes unless the PI or physician designee believes they represent a new medical condition when compared to baseline ECGs. In such cases an AE will be documented and the subject will be

followed for safety evaluations as appropriate. The following pre-existing conditions identified at enrollment will not be considered adverse events:

- sinus bradycardia;
- sinus arrhythmia;
- early repolarization;
- nonspecific ST-T wave pattern or changes, mild or moderate right axis deviation;
- first degree AV block (PR interval less than 210ms is acceptable);
- nonspecific intraventricular conduction delay (QRS, or average of triplicate QRS; less than 120ms is acceptable);
- short PR interval (where no delta wave), and indeterminate axis.

The Sponsor may review all or individual screening or Day -1 ECGs or may delegate to determine if meets intention of entry criteria goal of enrolling healthy normal study subjects.

Three ECG tracings are made pre-dose. At least 2 of the 3 tracings should be acceptable/normal per (correct) machine reading and all three must be consistent with otherwise healthy normal individuals.

If a post-dose ECG demonstrates a prolonged QTc interval (>500 ms) or an increase of at least 60ms from baseline average, 2 more tracings should be captured within 10 minutes. The averaged QTc value of these 3 will be used for decision making relative to the halting rules described in [Section 9.6](#).

In the event of a prolongation of QTc post dosing, the site will start telemetry monitoring of the subject and capture triplicate 12 lead ECG (3 tracings within a 5 minute period) every 30 minutes until the average for the triplicates has returned within 60ms of the baseline value at which time telemetry maybe discontinued. Persistent (1 hour or more) elevation in QTc (>500 ms) should prompt immediate consideration of transfer to appropriate emergency department for further evaluation, monitoring, and/or treatment.

In the event of a change in ECG wave forms consistent with a change in cardiac function or conduction when compared to baseline tracings, or in the event of a subject with possible cardiac related symptoms, repeat ECG should be obtained every 30 minutes until wave form change reverts to baseline appearance, or symptoms resolve, or are determined not to be cardiac in origin. Subjects with cardiac related symptoms associated with ECG changes will be transferred to appropriate emergency department for further evaluation and treatment.

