- Complete AE assessment (including SAEs) which will be recorded on AE source forms throughout the study and placed in the subject's clinic records. Data from the AE source form will be entered in the Electronic data capture (EDC) system. All AEs will be monitored until they are resolved or determined by the site PI to be medically stable.

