9.6 Study Halting Criteria

General:

- Any SAE
- Three or more subjects within a cohort, with the same Grade 2 event ;
- Any single Grade 3 or above finding (with the exception of aPTT as explained below);
- Evidence of hematemesis or hematochezia in 2 or more subjects
- Any other findings that, at the discretion of the PI, indicate that the study should be halted;

Electrocardiograph (ECG):

Two or more subjects within a cohort who meet any of the criteria below:

- PR: >220 ms
- QRS: >120 ms
- QTcF > 450 ms for men and >470 ms for women; or
- Change from baseline (average of pre-dose triplicate ECGs): QTcF >60 ms.

Decisions are to be based on an average QTcF value of triplicate ECGs. If an ECG demonstrates a prolonged QT interval, 2 more ECGs should be obtained over a 10 minute period. The averaged QTcF values of the 3 ECGs will then be used for decision making.

Laboratory criteria:

- Two or more subjects within a cohort have a Grade 3 increase in aPTT (confirmed on repeat) as defined by the FDA toxicity grading scale as modified for this study and as appropriate for the administration of UV-4B ([Appendix II](#)).

If any of the above events occur, the study will be halted and the SMC will review the available safety data to determine if the study should proceed as planned. If none of the events described above have been observed, dose escalation will proceed according to the protocol requirements.

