
(a) Abbreviated physical examination (general appearance, heart, lungs, skin and abdomen) Day -1, Day 8 and Day 10, and brief neurological examination (mental status, motor system, and sensory system) will be done Day -1 through Day 8 and Day 10. In addition, brief physical examinations focused on the examination of skin and oropharyngeal mucosa for evidence of bleeding and/or bruising (oral [gums] and cutaneous) will be performed Days -1 through 8, and Day 10 (including a Day 1 examination prior to the first dose and 30 minutes after the 1st dose). Symptom directed/targeted physical examinations will be done at other study time points based on subject symptoms.
 
(b) Vital signs (blood pressure and pulse rate including oral temperature and respiratory rate) taken after 10 minutes supine rest; should be taken after ECG recordings (1 hour window for pre-dose procedures).
 
(c) At pre-dose, and hourly up until 2 hours after the third dose of the investigational product per day.
 
(d) Blood pressure and pulse rate taken after 2 minutes in standing position. At pre-dose, and hourly up until 2 hours after the third dose of the investigational product per day.
 
(e) Females only.
 
(f) Postmenopausal females only.
 
(g) A subset of hematology (PLT count), serum chemistry (AST, ALT), and coagulation (INR, PT, aPTT) assessments will be collected prior to the first dose only.
 
(h) Fecal occult assessments will be performed on Day 1 starting approximately 6 hours post first dose on every stool sample. On Day 15, fecal occult assessment may be performed as per discretion of the PI, and, if positive, followed until resolution.
 
(i) Triplicate 12-lead ECGs at baseline (Day 1 pre-dose); single 12-lead ECGs obtained at the same time each day for all residential days. [ECGs will be repeated for confirmation of any stopping criteria and at the PI's discretion].
 
(j) Telemetry for at least 4 hours on Day -1 and starting at -0.5 hours prior to the first dose (Day 1) and continuously through 4 hours post the first dose. Starting at 0.5 hours prior to the 3rd dose on Day 7 continuously through 4 hours post dose. (PI discretion based on ECG results)
 
(k) Pre-dose on Day 1
 
(l) Blood samples for PK analysis will be collected at pre-dose (0 hour) and after the first dose at 0.25 (±5 min), 0.5 (±5 min), 1 (±10 min), 1.5 (±10 min), 2 (±10 min), 2.5 (±15 min), 3 (±15 min), 5 (±30 min), 6 (±30 min), 8 (±30 min) hours (8 hour sample to be collected immediately before the second dose),
 
(m) One trough sample daily within fifteen (15) minutes before the first dose
 
(n) Immediately (within fifteen minutes) before the final dose, and at 0.25 (±5 min), 0.5 (±5 min), 1 (±10 min), 1.5 (±10 min), 2 (±10 min), 2.5 (±15 min), 3 (±15 min), 5 (±30min), 6 (±30 min), 8 (±30 min), 10 (±30 min), 12 (±30 min), and 14 (±30 min) hours after the final dose;
 
(o) One sample.
 
(p) Vomitus occult assessment will be done on all vomitus
												

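### After QTc prolongation, half-hourly ECGs and telemetry can end while QTc is still above 500 ms if the baseline exceeds 440 ms (minor, rare)

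*Protocol*

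**What the plan says.** Protocol 9.1.3 sets two limbs for repeating a post-dose tracing: "If a post-dose ECG demonstrates a prolonged QTc interval (>500 ms) or an increase of at least 60ms from baseline average". Either limb calls for two more tracings, and the mean of the three feeds the halting decision.

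The next paragraph covers what follows a prolongation. The site starts telemetry and takes triplicate 12-lead ECGs "every 30 minutes until the average for the triplicates has returned within 60ms of the baseline value at which time telemetry maybe discontinued". The sentence after it returns to the absolute level: "Persistent (1 hour or more) elevation in QTc (>500 ms) should prompt immediate consideration of transfer to appropriate emergency department". A further paragraph requires ECGs every 30 minutes for waveform change suggesting altered cardiac function or conduction, or for possible cardiac symptoms.

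On entry, exclusion criterion 8 (Protocol 5.2) reads: "Abnormal ECGs; however, abnormal readings for the following benign conditions will be acceptable for the study". The list that follows gives numbers for axis, PR and QRS but none for QTc. A previously recorded finding judged medically insignificant may also be accepted. For the Day 1 pre-dose triplicate, 9.1.3 says: "At least 2 of the 3 tracings should be acceptable/normal per (correct) machine reading and all three must be consistent" with healthy normal individuals. Again there is no QTc figure.

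**The concern.** The rule can be entered on either of two limbs but left on only one. The level above 500 ms is the one at which the protocol asks staff to consider emergency transfer, yet the exit does not mention it. Followed as written, required half-hourly ECGs could stop while QTc is still above that level.

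The transfer sentence depends on knowing that the elevation has lasted an hour, and that takes repeat ECGs. If the exit is met sooner, the required tracings that would show persistence end. The next scheduled ECG is a single daily tracing (Protocol 7.3.2; Appendix IV, footnote (i)), while dosing continues every 8 hours (Protocol 6.2.1).

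**Working it through.** The documents give no figure to reproduce here. The check is an inequality.

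**Inputs**
- B: baseline QTc, from the Day 1 pre-dose triplicate (Protocol 9.1.3); q: post-dose triplicate average. Correction is Fridericia (Protocol 9.4).
- Prolonged: q > 500, or q − B ≥ 60 (9.1.3).
- Exit: q − B ≤ 60 (9.1.3, reading *within 60 ms* as including 60).
- The paragraph holding the exit does not define its own trigger. Taking the two limbs from the paragraph before it is an inference.

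**When can the exit be met above 500 ms?** Both conditions require 500 < q ≤ B + 60. Such a q exists only if B + 60 > 500, that is, B > 440. In whole milliseconds:

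| B (ms) | Largest q meeting the exit (B + 60) | Values above 500 that meet it |
|---|---|---|
| 420 | 480 | none |
| 440 | 500 | none |
| 441 | 501 | 501 |
| 445 | 505 | 501–505 |
| 450 | 510 | 501–510 |
| 460 | 520 | 501–520 |
| 470 | 530 | 501–530 |

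The width of the overlap is B − 440. If *within 60 ms* means strictly less than 60, the upper ends fall by 1 ms and the first affected whole-ms baseline is 442 rather than 441.

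**Which baselines are plausible?** No entry rule gives a ceiling, so this is an assumption shown as a range. SAP 10.7.6 flags QTcF above 450 ms in listings; at 450 the overlap is 10 ms. The halting rule (Protocol 9.6) and the SAP outlier categories use 450 ms for men and 470 ms for women; at 470 the overlap is 30 ms. None of these figures is an eligibility limit.

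**Two kinds of subject, both with B = 450**
- *Falls back.* A triplicate averages 511 (511 − 450 = 61, outside the band). The one 30 minutes later averages 505 (505 − 450 = 55). The average has come back inside 60 ms, so the exit is met after half an hour, with QTc above 500 ms and the one-hour point not reached.
- *Never outside the band.* The average is 505 from the start, a rise of 55. It is prolonged on the absolute limb only. Whether the exit applies is unclear, because nothing has *returned*.

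**With 500 ms added to the exit**, the largest value that can meet it is the smaller of B + 60 and 500. No value above 500 ms meets it at any baseline. For B ≤ 440 the added limit has no effect, since B + 60 is already at most 500.

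**The case against.** The best counter-argument is textual. The protocol attaches the word *prolonged* to values above 500 ms, and the monitoring paragraph begins with a prolongation of QTc. A triplicate still above 500 ms could be seen as calling for monitoring afresh. *Returned* also implies that the average had been outside the 60 ms band. A reader might infer that any subject with a baseline above 440 ms who passes 500 ms on a rise below 60 ms is released at the first triplicate. The documents do not support that as a settled reading; for this subject the text is ambiguous. The argument is weaker for the subject who falls back into the band: the exit wording then fits, and continued monitoring depends on treating the same tracing as a new trigger.

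Other duties also bear on the point:
- Protocol 9.6 says "If an ECG demonstrates a prolonged QT interval, 2 more ECGs should be obtained over a 10 minute period". This confirms a value; it does not follow its course. ECG halting needs two or more subjects in a cohort.
- Appendix IV, footnote (i), says "ECGs will be repeated for confirmation of any stopping criteria and at the PI's discretion". It sets no frequency.
- Protocol 7.3.2 says "All AEs will be monitored until they are resolved or determined by the site PI to be medically stable", and 9.2.3 and 9.4 are similar. None fixes an ECG interval.
- The 30-minute rule for waveform change or cardiac symptoms does fix an interval and has no 60 ms exit. It protects any subject with those findings, but does not name QTc above 500 ms alone.
- The investigator or a designee reviews every ECG and may continue monitoring, stopping telemetry is permitted rather than required, and the transfer sentence is not conditional on the exit.

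These points stand as mitigation. They leave the required schedule able to end before one hour of persistence can be judged.

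**Conclusion.** The concern holds as a minor, rare safety gap. The 440 ms threshold follows exactly from 500 − 60. The overlap is B − 440 ms wide: 10 ms at a baseline of 450 and 30 ms at 470. Screening for healthy volunteers with acceptable ECGs should make such baselines uncommon, but no stated limit excludes them and the documents give no baseline QTc distribution, so a frequency cannot be calculated.

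The conclusion rests on two assumptions: that the two limbs in 9.1.3 define the prolongation that starts monitoring, and that *within 60 ms* includes 60 (the strict reading moves the result by 1 ms).

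Two stronger inferences fail. The protocol does not tell sites to abandon a subject above 500 ms, because the transfer sentence, the symptom and waveform rule and investigator discretion all remain. Nor is the analysis affected: SAP 10.7.6 runs its outlier analysis on all post-dose readings, including repeat and unscheduled ones, so a subject with any value above 500 ms is already in that category.

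**What to change.** In Protocol 9.1.3, make the exit depend on both limbs. Half-hourly triplicates continue until their average is within 60 ms of baseline and is also no longer above 500 ms; only then may telemetry be discontinued. This closes the fall-back case and settles the ambiguous one, so that both possible sites apply the same rule.

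The cost is one clause in one sentence, plus a few more ECGs and longer telemetry in rare subjects. Nothing changes for baselines at or below 440 ms, and the SAP needs no change.
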